7.6.1.5 Subgroup Analysis

Subgroup analyses for co-primary endpoints will be performed using mITT population in the following subgroups, defined based on the baseline values:

- Age [<65 at randomization; ≥65 years at randomization]
- Gender [M; F]
- Race [White; Non-White]
- Region [North America; Europe; Rest of World]
- 6-MWD*
- TTR mutation*
- NYHA class* [I and II; III] at stratification*
- PND score [0; I; II]

Subgroups with > 2 levels may be collapsed due to sparse data at a level prior to unblinding and database lock. The decision to collapse will be justified and documented prior to unblinding.

An unstratified Finkelstein and Schoenfeld Joint Rank Test will be used for the co-primary endpoint of 6-MWD within each subgroup. An ANCOVA model will be used for the co-primary endpoint of percent reduction in serum TTR burden from baseline over 18 months within each subgroup. Covariates include treatment group and baseline TTR in the model.

7.6.2 Secondary Efficacy Analysis

Analyses will be performed in the mITT population for all secondary efficacy endpoints. Type I error control for secondary endpoints will be achieved by the following pre-specified hierarchical order:

- Composite CV mortality and CV hospitalization
- Change from baseline in NYHA class
- Change from baseline in KCCQ Overall Summary Score
- CV mortality
- CV hospitalization
- All-cause mortality

If and only if a comparison of treatment group is significant ($p \le 0.05$), then the next endpoint in the

^{*}Categorization of stratification factors (6-MWD, TTR mutation and NYHA class) will use the values from eCRF. Patients will be categorized into a region based upon the location of the site.

Version: 1.0

Alnylam Protocol No. ALN-TTRSC-004

hierarchy may be formally tested.

The classification of mortality and hospitalization events will be determined by an independent Clinical Adjudication Committee (CAC).

7.6.2.1 Composite CV Mortality and CV Hospitalization

The primary analysis of the composite of CV mortality and CV hospitalization will be based on stratified Finkelstein and Schoenfeld Joint Rank Test. All pairs of patients will be compared within a stratum. A patient will be compared with another patient in a step-wise fashion to identify the patient in the pair with the better outcome:

Step 1: Compare time to CV mortality; If it cannot be determined which patient died earlier due to CV mortality, then go to Step 2

Step 2: Compare number of CV hospitalizations at the latest common study visit

Details of the comparisons of time to CV death and number of CV hospitalizations are described in Appendix I.

Additional descriptive analyses for each component by treatment group will be generated. The number of patients (%) with a CV mortality event will be present at each visit interval [>-0- \le 6 months, >6- \le 12 months, >12- \le 18 months and >0- \le 18 months].

The cumulative number of CV hospitalizations per patient reported during each visit intervals [>0 to \leq 6 months, >6 to \leq 12 months or >12 to \leq 18 months and >0 to \leq 18 months] will be presented for each treatment group. Additionally, at each visit interval, the cumulative number of CV hospitalizations and percentage of patients with a CV hospitalization event will be tabulated.

7.6.2.2 Change in NYHA from Baseline

The primary analysis of change in NYHA from baseline will be based on stratified Finkelstein and Schoenfeld Joint Rank Test. All pairs of patients will be compared within a stratum. A patient will be compared with another patient in a step-wise fashion to identify the patient in the pair with the better outcome:

Step 1: Compare time to death;
If it cannot be determined which patient lived longer, then go to Step 2

Step 2: Compare change in NYHA from baseline to the latest common study visit

Details of the comparisons of time to death and change in NYHA are described in Appendix I.

Descriptive statistics displaying a shift table of baseline NYHA class category [range: 1-4] to each post-baseline visit categories [range: 1-4] will be generated. An overall shift of the baseline to worst post-baseline NYHA class category will be presented as well for each treatment group.

7.6.2.3 Change in overall summary score from Baseline - KCCQ

The primary analysis of change in overall summary score from baseline will be based on stratified Finkelstein and Schoenfeld Joint Rank Test. All pairs of patients will be compared within a stratum. A patient will be compared with another patient in a step-wise fashion to identify the patient in the pair with the better outcome:

Step 1: Compare time to death;

If it cannot be determined which patient lived longer, then go to Step 2

Step 2: Compare change in overall summary score at the latest common study visit

Note: The overall summary score is calculated based on responses from the KCCQ questionnaire. The questionnaire summarizes 8 subscales and 2 summary scores (see Appendix III for further details).

Details of the comparisons of time to death and change in overall summary score are described in Appendix I.

Descriptive statistics of overall summary score and change in overall summary score will be generated for each treatment group at baseline and each post-baseline visit. These analyses above will be repeated for each of the 8 subscales and clinical summary score used in the KCCQ questionnaire.

7.6.2.4 CV Mortality

The primary analysis for time from date of first dose of study drug to CV mortality event will be based upon a stratified log-rank test to compare treatment groups. Definition details for CV mortality are located in Appendix I.

The distribution of time from date of first dose of study drug to CV mortality for each treatment group will be generated using Kaplan-Meier (KM) plot. For each percentile (25th, 50th, 75th) if reached, an estimate of time from date of first dose of study drug to CV mortality and the associated 95% confidence intervals using Brookmeyer-Crowley methodology will be presented for each treatment group.

In addition, a stratified Cox proportional hazard model will be used to analyze time to CV mortality, with treatment group as the model covariate. The hazard ratio and associated 95% confidence intervals of the hazard ratio will be presented.

7.6.2.5 CV Hospitalization

The primary analysis for time from date of first dose of study drug to CV hospitalizations will be based upon a stratified Cox proportional hazard model using Anderson-Gill method to model recurrent events. To account for the correlation of CV events within each subject the Cox proportional hazards model will specify robust sandwich estimate for the covariance matrix. The hazard ratio and associated 95% confidence interval of the hazard ratio will be presented. In addition, we will calculate the cumulative hazard function every 6 months using Nelson-Aalen estimator.

Version: 1.0

Alnylam Protocol No. ALN-TTRSC-004

7.6.2.6 All-cause Mortality

The primary analysis for time from date of first dose of study drug to all-cause mortality event will be based upon a stratified log-rank test to compare treatment groups. Definition details for All-cause Mortality are located in Appendix I.

The distribution of time from date of first dose of study drug to all-cause mortality for each treatment group will be generated using Kaplan-Meier (KM) plot. For each percentile (25th, 50th, 75th) if reached, an estimate of time from date of first dose of study drug to CV mortality and the associated 95% confidence intervals using Brookmeyer-Crowley methodology will be presented for each treatment group.

In addition, a stratified Cox proportional hazard model will be used to analyze time to all-cause mortality, with treatment group as the model covariate. The hazard ratio and associated 95% confidence intervals of the hazard ratio will be presented.

The cumulative number of patients with an all-cause mortality event and associated percentage for each treatment group will be displayed. In addition, the total number of patients (and associated percentage) in each type of mortality event (CV, HF, not CV nor HF) will be displayed by treatment group.

7.6.3 Exploratory Efficacy Analysis

7.6.3.1 Echocardiogram (ECHO) Parameters

Descriptive statistics of actual value, change from baseline and percent change from baseline for selected ECHO parameters will be generated for each treatment group by visit.

Selected ECHO parameters are located in Appendix V.

7.6.3.2 Karnofsky Performance Status

Karnofsky Performance Status [KPS] will be categorized into 3 main categories (1=Able to carry on normal activity and to work, no special care [KPS range: 80-100], 2=Unable to work; able to live at home and care for most personal needs; varying amount of assistance [KPS range: 50-70], 3=Unable to care for self; requires hospital care; disease may be progressing rapidly [KPS range: 0-40]).

Descriptive statistics displaying a shift table of baseline KPS class category [range: 1-3] to each post-baseline visit categories [range: 1-3] will be generated. An overall shift of the baseline to worst post-baseline KPS class category will be presented for each treatment group

A frequency of each KPS category [0-100] will be generated for each treatment group at each visit.

7.6.3.3 Troponin T and I, and NT proBNP Levels

Descriptive statistics of actual value, change from baseline and percent change from baseline for each cardiac biomarker will be generated for each treatment group by visit.

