3.3. Efficacy Endpoints

3.3.1. Primary endpoints:

The co-primary endpoints of the study are to evaluate the difference between the ALN-TTRSC and placebo groups for:

- 1. Change in 6-MWD at 18 months compared to baseline
- 2. Percent reduction in serum TTR burden over 18 months

3.3.2. Secondary endpoints:

The secondary endpoints of the study are to determine the effect of ALN-TTRSC on various clinical parameters by assessing the difference between the ALN-TTRSC and placebo groups at 18 months for:

- Composite CV mortality and CV hospitalization
- Change in New York Heart Association (NYHA) class (Appendix 1) compared to baseline
- Change in Kansas City Cardiomyopathy Questionnaire (KCCQ) compared to baseline
- Cardiovascular (CV) mortality
- CV hospitalization

Confidential

All-cause mortality

3.3.3. Exploratory endpoints:

The exploratory endpoints of the study are to determine the difference between the ALN-TTRSC and placebo groups in the change from baseline at 18 months in the following measurements:

- EuroQOL (EQ-5D) questionnaire
- Echocardiogram parameters
- Karnofsky Performance Status (Appendix 2)
- Troponin T and I, and N-terminal prohormone of B-type natriuretic peptide (NT proBNP) levels
- Cardiac magnetic resonance imaging (CMR) parameters (only at selected sites)
- 99m Technetium scintigraphy parameters (only at selected sites)
- Amyloid in abdominal wall fat pad aspirates
- Polyneuropathy Disability (PND) Score (Appendix 3)
- Modified body mass index (mBMI)
- Estimated glomerular filtration rate (eGFR)
- HF hospitalization

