3.3 Exploratory Efficacy Endpoints

The exploratory endpoints of the study are to evaluate differences between revusiran and placebo at 18 months for:

- EuroQoL 5 Domains, 5 Levels of response (EQ-5D-5L) questionnaire
- Echocardiogram (ECHO) parameters
- Karnofsky Performance Status
- Troponin T and I, and N-terminal prohormone of B-type natriuretic peptide (NT proBNP) levels
- Cardiac magnetic resonance imaging (CMR) parameters (only at selected sites)
- Technetium-99m scintigraphy parameters (only at selected sites)
- Amyloid in abdominal wall fat pad aspirates
- Polyneuropathy Disability (PND) Score
- Modified body mass index (mBMI)
- Estimated glomerular filtration rate (eGFR)
- Heart Failure (HF) hospitalization

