7 STATISTICAL METHODS

7.1 General Principles

All data processing, summarization and analyses will be performed using the SAS Version 9.3 (or later) of the SAS® statistical software package.

All data collected will be sorted and presented in listings by treatment group, site, patient identification, assessment, relative day (see Section 6.1 for definition) and visit (where applicable), unless otherwise specified.

Data will be presented in summary tables by treatment group (revusiran, placebo), assessment and visit (where applicable).

Descriptive summary statistics for continuous variables will include the number of patients/observations (N), mean, standard deviation (SD), median and range (minimum, maximum).

Descriptive summary statistics for categorical variables will include frequency counts and percentages for each category [n (%)]. A category of missing will be included if the number missing is greater than zero. Unless stated otherwise in the table shells, the denominator for percentage calculations will be the number of patients in the analysis population.

All statistical tests will be 2-sided and performed at the 5% significance level, unless otherwise specified. Confidence intervals of 95% will be provided where appropriate.

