Complete Cases (CC) analysis will include all patients with non-missing TTR results at month 18. The mixed-effect model used in the sensitivity #2 will be employed. No imputation will be considered. The dependent variable will be log transformed.

Below are additional descriptive analyses of serum TTR. These analyses will be unstratifed using the mITT population.

Serum TTR: Descriptive statistics of serum TTR values, change from baseline in serum TTR values and percent reduction in TTR values will be presented for each treatment group. An additional summary table of descriptive statistics for the maximum percentage reduction in TTR for each treatment group will also be presented.

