7.6.3.10 Heart Failure (HF) Hospitalization

7.6.3.9 Estimated Glomerular Filtration Rate (eGFR)

The time from date of first dose of study drug to HF hospitalization will be a stratified Cox proportional hazard model using Anderson-Gill method to model recurrent events. To account for the correlation of CV events within each subject the Cox proportional hazards model will specify a robust sandwich estimate for the covariance matrix. The hazard ratio and associated 95% confidence interval of the hazard ratio will be presented.

The cumulative number of HF hospitalizations per patient reported during each visit intervals [>0 to \leq 6 months, >6 to \leq 12 months or >12 to \leq 18 months and >0 to \leq 18 months] will be presented for each treatment group. Additionally, at each visit interval, the cumulative number of HF hospitalizations and percentage of patients with a HF hospitalization event will be tabulated.

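### The NT-proBNP and troponin endpoints are defined as a between-arm difference at 18 months, but the SAP plans only by-arm descriptive statistics, with no contrast, confidence interval or baseline covariate

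*SAP*

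**What the plan says.** Protocol 3.3.3 states that the exploratory endpoints are "to determine the difference between the ALN-TTRSC and placebo groups in the change from baseline at 18 months in the following measurements", and the list includes troponin T and I and NT-proBNP. SAP 3.3 repeats the aim: "The exploratory endpoints of the study are to evaluate differences between revusiran and placebo at 18 months for" the same list.

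The analysis in SAP 7.6.3.3 is one sentence, applied at each visit: "Descriptive statistics of actual value, change from baseline and percent change from baseline for each cardiac biomarker will be generated for each treatment group". SAP 7.1 defines descriptive statistics for continuous variables as N, mean, SD, median and range. It adds a general line, "Confidence intervals of 95% will be provided where appropriate", which is not tied to any biomarker, estimate or model.

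The biomarkers are scheduled at Screening, at Day 0 and at months 3, 6, 9, 12, 15 and 18 (protocol Table 1-1), and are measured centrally (protocol 7.3.11). If they fall under the last baseline rule of SAP 6.1, their baseline is the last assessment before the first dose. That baseline is used to form change and percent change, but nowhere as a covariate.

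**The concern.** The quantity that the documents name as the endpoint is not one that the plan produces. A reader of the study report would see two columns of summaries per visit and would have to judge the difference, and its uncertainty, by eye.

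The scale matters too. Percent change is asymmetric: a doubling counts as +100% and a halving as -50%. If the values are right-skewed, the mean percent change is positive when the typical patient has not changed, and it rises with variability alone. Two arms that differ only in spread would then show different means.

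Because no contrast is fixed in advance, the choice among raw, percent, median and log-scale comparisons is left until after unblinding.

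**Working it through.** **1. The plan's own figure.** No sizing figure exists for the biomarkers; the only one is for 6-MWD (SAP 2.3): 120 vs 60 patients, 0.55 SD, deaths of 13% vs 20%, about 90% power. A simulated unstratified joint-rank test with deaths ranked worst gives 0.884 with those death rates and 0.900 with a hazard ratio of exactly 0.6. The dropout step also reproduces: 180/0.90 = 200. There is no numerical error here. The same inputs give the survivors used below: 120 × 0.87 = 104.4, taken as 104, and 60 × 0.80 = 48.

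**2. Endpoint against analysis.**

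| Variable | Planned analysis | Between-arm estimate with CI |
|---|---|---|
| NT-proBNP, troponin T and I (exploratory, SAP 7.6.3.3) | By-arm descriptive statistics | None specified |
| HF hospitalization (exploratory, SAP 7.6.3.10) | "stratified Cox proportional hazard model using Anderson-Gill method to model recurrent events" | Hazard ratio, 95% CI |
| Serum TTR (co-primary, SAP 7.6.1.4 Sensitivity #2) | MMRM on log fold change, adjusted for baseline and strata | Adjusted mean difference, 95% interval |

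The SAP thus specifies a contrast for one other exploratory endpoint, and already contains a suitable log-scale model.

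**3. Effect of skew on the mean.** Assumption: the ratio of follow-up to baseline is log-normal with median m and log-scale SD s. The documents give neither a distribution nor an SD.

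- Mean percent change = 100 × [m × exp(s²/2) - 1]
- Median percent change = 100 × (m - 1)

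With no median change (m = 1):

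| s | exp(s²/2) | Mean % change | Median % change |
|---|---|---|---|
| 0.3 | 1.046 | +4.6 | 0 |
| 0.5 | 1.133 | +13.3 | 0 |
| 0.7 | 1.278 | +27.8 | 0 |
| 0.9 | 1.499 | +49.9 | 0 |

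Arms with equal medians but s = 0.5 and 0.7 would differ in mean percent change by 27.8 - 13.3 = 14.5 points. With a true median fall of 20% (m = 0.8) and s = 0.8, the mean is 0.8 × exp(0.32) - 1 = 0.8 × 1.377 - 1 = +10%, so its sign reverses. The median stays at -20%.

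**4. What a log-scale contrast would give (illustration only).** Inputs: log-normal baseline and month-18 values, true revusiran/placebo ratio 0.75, 104 vs 48 survivors, log-SD 0.8 to 1.0, baseline correlation 0.6 to 0.8. Since s = log-SD × √(2(1 - correlation)), s runs from 0.8 × √0.4 = 0.51 to 1.0 × √0.8 = 0.89. Simulated power at two-sided 5%:

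| Contrast | Power over the region |
|---|---|
| Baseline-adjusted log ANCOVA | about 54-93% |
| t-test on percent change | about 27-85% |
| t-test on raw change | about 24-63% |

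The gap between log ANCOVA and percent change narrows as s falls. In a separate simulation with s = 0.40 they had power 0.98 and 0.96; at s = 0.80, 0.62 and 0.34.

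In that second set, the 95% interval for the ratio was the estimate divided and multiplied by 1.14 (s = 0.40) to 1.28 (s = 0.80). Around 0.75 that is 0.66 to 0.86 at best and 0.59 to 0.96 at worst. The by-arm medians stayed near their true values throughout, at about -8% and +23%.

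**The case against.** The strongest reply is that these endpoints are exploratory and that descriptive reporting is the SAP's general approach to them, from echocardiography to EQ-5D-5L; HF hospitalization is the exception. The log-scale TTR model is a sensitivity analysis of a co-primary endpoint and sets no standard for exploratory ones. That is fair, and it keeps the point small. It does not remove the mismatch between a stated between-group aim and a plan with no between-group estimate.

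Four stronger readings are tempting, and the documents do not support them.

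- *That the planned summaries as a whole are distorted by skew.* Actual values and medians are planned as well. Median percent change is essentially exp(median log-ratio) - 1, so the asymmetry does not affect it. Only the mean and SD are exposed, and only if the data are skewed.
- *That the plan makes the between-arm difference unobtainable.* An unadjusted difference can be derived from the by-arm N, mean and SD. It is simply not planned, adjusted or given an interval.
- *That the plan loses power.* SAP 7.6.3.3 plans no test, so the power figures compare contrasts that someone might choose.
- *That these biomarkers are the main objective evidence of a cardiac effect.* The protocol does not say so. They are one of eleven exploratory items, next to echocardiography, CMR and scintigraphy.

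There is also a fair objection to the remedy. SAP 7.6.1.2 says that its 6-MWD MMRM treats data missing after death as missing at random. A biomarker MMRM would inherit that assumption and could not be described as an estimate in survivors.

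**Conclusion.** The point holds as a gap between endpoint and analysis: a between-arm difference at 18 months is named, and no contrast, interval or baseline-adjusted model is planned to estimate it. This rests on the documents alone.

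The size of the skew problem rests on assumed log-normal data. With no median change, the mean percent change would be +5% to +50% for s from 0.3 to 0.9, while the planned median would be correct. The power comparison is illustrative and says nothing about a test in the SAP.

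The co-primary tests, the secondary hierarchy and type I error are untouched. This is a worthwhile low-cost improvement and no more.

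**What to change.** Amend SAP 7.6.3.3 before unblinding:

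- For each of NT-proBNP, troponin T and troponin I, add an exploratory model of log(post-baseline/baseline) with treatment, visit, treatment-by-visit, log baseline and the SAP's analysis strata (TTR mutation and 6-MWD, SAP 7.6). This adapts Sensitivity #2 of SAP 7.6.1.4; the baseline term changes from the TTR level to log baseline.
- Report the adjusted geometric mean ratio between arms with a 95% confidence interval at each visit, with month 18 as the main one.
- Add geometric means to the by-arm summaries and keep the medians.
- State that the MMRM treats data missing after death as missing at random, as SAP 7.6.1.2 does. If an estimate in survivors is wanted, use a month-18 log-scale ANCOVA in patients alive and sampled, and label it so.
- Say how results below the quantification limit enter the log. The SAP has one rule for TTR (half the limit, 6.2.1) and another for laboratory values (the limit itself, 7.7.2).

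The cost is a short SAP amendment and a little more output. No new data are needed.

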7.6.3.4 Cardiac Magnetic Resonance (CMR) Imaging Parameters

Descriptive statistics of actual value, change from baseline and percent change from baseline for selected CMR parameters will be generated for each treatment group by visit.

Note: This procedure is only conducted at selected sites and only allowed to be performed on patients without contraindications (ie, pacemarkers, severe renal failure with eGFR, defibrillators or allergy to gadolinium). A summary of the sites that were selected to perform the test will be tabulated.

Selected CMR parameters are located in Appendix VI.

